Exclusion Criteria: previous allergic reaction or absolute contraindication to topical chlorhexidine gluconate or any other study product ingredient, dermatologic disorders around the surgical site, signs of other infections, age under 18, pregnancy

e. If participants will comprise more than one group or stratification, describe each group (e.g., treatment/intervention, placebo, controls, sham treatment) **and** provide the number of participants anticipated in each group.

Control group – 160 patients who will receive only standard skin preparation prior to surgery.
Intervention group 1 – 160 patients who will be administered 2% Chlorhexidine Gluconate wipes once on the night prior to surgery and once on the day of surgery in addition to standard skin preparation.
Intervention group 2 – 180 patients who will be administered Theraworx™ wipes once on the night prior to surgery and once on the day of surgery in addition to standard skin preparation.

f. Indicate which, if any, of the special populations listed below will be involved in the protocol. Include the Special Populations Review Form (SPRF) if indicated.

- Pregnant Women: Attach [SPRF—Pregnant Women, Fetuses, Neonates/Nonviable Neonates](#)
- Fetuses: Attach [SPRF—Pregnant Women, Fetuses, Neonates/Nonviable Neonates](#)

FOR 200 Revised 4/23/2020 Page 11 of 16 07/29/19

- Neonates/Nonviable Neonates: [SPRF—Pregnant Women, Fetuses, Neonates/Nonviable Neonates](#)
- Prisoners: Attach [SPRF—Prisoners](#)
- Minors (<18 years old): Attach [SPRF—Minors](#) **NOTE:** For BVAMC Research <19 years old
- Employees or students at institution where research conducted
- Persons who are temporarily decisionally impaired
- Persons who are permanently decisionally impaired
- Non-English Speakers

For each box checked, describe why the group is included and the additional protections provided to protect the rights and welfare of these participants who are vulnerable to coercion: There's no reason to exclude participants who are employees or students at UAB. We will explain that the decision to participate or not in this study will not affect the participant's relationship with UAB and the investigators. g. List any persons other than those directly involved in the protocol who will be at risk. If none, enter "None": **None**

h. Describe the recruitment process (e.g., medical record review, referrals, letter of invitation, existing patients) that will be used to seek potential participants (e.g., individuals, records, specimens). Research recruitment by non-treating physicians/staff may require completion of [Partial Waiver of Authorization for Recruitment/Screening](#). **[name] and [name] will screen their pre-surgical clinic patients for potential participants though their clinic encounters and ask patients if they are interested in participating. Orthopaedic research fellows, will provide explanations to patients and consent patients for the study in Highlands hospital following a guideline set by [name]. Additionally, Drs. [name] and [name] may enroll their own patients if clinical time permits. Other orthopedic surgeons at UAB Highlands hospital may be invited to participate in recruiting patients for this study in the future if needed to achieve an adequate number of participants. They will be fully instructed on all recruitment guidelines and procedures.**

i. If you will use recruitment materials (e.g., advertisements, flyers, letters) to reach potential participants, attach a copy of each item. If not, identify the source (e.g., IRB Protocol Number for approved databases) from which you will recruit participants. **Participants will be recruited from [name] and [name] clinic**

j. Describe the screening process/procedures for potential participants. **[name] and [name] will screen their pre-surgical clinic patients for potential participants though their clinic encounters by asking if patients are interested in participation and meet inclusion/exclusion criteria. If patient is interested and eligible, a research fellow, research nurse, or [name] will proceed to consent the patients.**

17. Protocol Procedures, Methods, and Duration - in nontechnical, lay language

a. Describe the procedures for all aspects of your protocol. Tell us what you are doing.

This study is a randomized study that will include three groups: a control group, intervention group 1 that will be administered topical 2% chlorhexidine gluconate (CHG) wipes once the night before

surgery and once on the day of surgery, and intervention group 2 that will be administered topical Theraworx™ wipes once the night before surgery and once on the day of surgery. After IRB is approved, 500 participants (160-180 per group) will be collected for the prospective study. Patients will be randomized into groups using a random number list generated in excel, which will be consulted by a research nurse or research fellow, who will instruct the patient in the use of the product related to their group assignment. [name] or [name] will perform orthopedic surgery on the participants without knowledge of their group assignment. Patients will be assessed for regimen compliance by survey. At clinic visits, patients will be assessed for the presence of surgical site infection, wound healing and scar formation, pain scores, and will be asked to complete a self-administered patient satisfaction questionnaire.

FOR 200 Revised 4/23/2020 Page 12 of 16 07/29/19

- b. What is the probable length of time required for the entire protocol (i.e., recruitment through data analysis to study closure)? **2 years**
- c. What is the total amount of time each participant will be involved? **1 year**
- d. If different phases are involved, what is the duration of each phase in which the participants will be involved? If no phases are involved, enter "None." **None**
- e. List the procedures, the length of time the procedure takes, the total # of times the procedure is performed, and indicate whether each is performed solely for research or would already be performed for treatment or diagnostic purposes (routine care) for the population.
-Insert additional table rows as needed.
-If procedure is sometimes research and sometimes routine care, include on separate lines with number of times as each.

Procedure	Length of Time Required of Participants	Total # of Times the Procedure is Performed	Research (Res) –OR– Routine Care
Orthopedic surgery	1 day	1	 Res  Routine
Skin product application	5 min	2	 Res  Routine
Patient Survey	5 min	1	 Res  Routine

- f. Will an interview script or questionnaire be used? Yes No **If Yes, attach a copy.**
- g. Will participants incur any costs as a result of their participation? Yes No **If Yes, describe the reason for and amount of each foreseeable cost.**
- h. Will participants be compensated? Yes No **If Yes, complete i-v.**
- i. Type: (e.g., cash, check, gift card, merchandise):
- ii. Amount or Value:
- iii. Method (e.g., mail, at visit):
- iv. Timing of Payments: (e.g., every visit, each month):
- v. Maximum Amount of Compensation per Participant:

18. Benefits

Describe the potential benefits of the research. **The research has the potential to benefit the U.S. health care system, surgeons, and patients. In recent years, surgical site infections occur in about 2% of all patients undergoing orthopedic procedures. Surgical site infections often necessitate longer hospital stays, increased use of antibiotics, and even revision surgery and puts economic burden on patients, physicians, and hospitals. This research aims to highlight the effectiveness of Theraworx™ wipes to reduce the rate of surgical site infections and to introduce the wipes as a part of the standard skin preparation for various orthopedic procedures.**

19. Risks - in nontechnical, lay language

- a. List the known risks for participants as a result of participation in the research. This should not include the minimal risk of loss of confidentiality. However, it should include any physical, psychological, social, economic, and/or legal risks. If there is a greater than minimal risk of loss of confidentiality describe why this is so. Do not list risks associated with the standard-of-care procedures.

FOR 200 Revised 4/23/2020 Page 13 of 16 07/29/19

NOTE: Risks included here should be included in the consent form or information sheet, as applicable. The major risk of this study is possible allergic or serious skin reaction to the 2% topical Chlorhexidine Gluconate or Theraworx™ wipes. Up to 10% may experience dryness, itching, or rash on the application site. Very rarely (less than 1% of patients), patients may experience a serious allergic reaction within minutes after the application of the wipe.

- b. Estimate the frequency, severity, and reversibility of each risk listed. N/A
- c. Is this a therapeutic study or intervention? Yes No **If Yes, complete i.-iii.**
- Describe the standard of care in the setting where the research will be conducted:
 - Describe any other alternative treatments or interventions:
 - Describe any withholding of, delay in, or washout period for standard of care or alternative treatment that participants may be currently using:
- d. Do you foresee that participants might need additional medical or psychological resources as a result of the research procedures/interventions? Yes No **If Yes**, describe the provisions that have been made to make these resources available.
- e. Do the benefits or knowledge to be gained outweigh the risks to participants? Yes No **If No**, provide justification for performing the research:

20. Precautions/Minimization of Risks

- a. Describe precautions that will be taken to avoid risks and the means for monitoring to detect risks. **There are minimal risks and risk of randomization involved with this study. Even so, patients will be in the clinic under the care of the nursing staff and the operating team. Patients will be closely monitored for any adverse reaction due to the topical products before their surgery begins. Patients will also be informed about the possibility of adverse reactions and instructed to discontinue use and seek immediate medical attention if they experience any signs or symptoms of serious adverse effects or severe allergic reactions. Patients with contraindications to any of the interventions will be excluded from the study.**

If the protocol involves drugs or devices skip Items 20.b. and 20.c. and go to Item 21. Instead, include this information in the [Drug Review Sheet](#) or [Device Review Sheet](#), as applicable.

- b. If hazards occur to an individual participant, describe (i) the criteria that will be used to decide whether that participant should be removed from the protocol; (ii) the procedure for removing such participants when

necessary to protect their rights and welfare; and (iii) any special procedures, precautions, or follow-up that will be used to ensure the safety of other currently enrolled participants.

- c. If hazards occur that might make the risks of participation outweigh the benefits for all participants, describe (i) the criteria that will be used to stop or end the entire protocol and (ii) any special procedures, precautions, or follow-up that will be used to ensure the safety of currently enrolled participants. N/A

21. Informed Consent

- a. Do you plan to obtain informed consent for this protocol? Yes No **If Yes**, complete the items below.

If No, complete and include the [Waiver of Informed Consent](#) or [Waiver of Authorization and Informed Consent](#), as applicable.

*For research being conducted at the BVAMC, the UAB Consent waiver form must be completed and submitted with the HSP.

- b. Do you plan to document informed consent (obtain signatures) for this protocol? Yes No **If Yes**, complete the items below.

If No, complete the items below **and** include the [Waiver of Informed Consent Documentation](#).

FOR 200 Revised 4/23/2020 Page 14 of 16 07/29/19

- c. How will consent be obtained? **Interview**,

- d. Who will conduct the consent interview? **[name], [name]**

- e. Who are the persons who will provide consent, permission, and/or assent? **Patients**

- f. What steps will be taken to minimize the possibility of coercion or undue influence? **Patients will not be financially compensated, and each patient will be asked if they are interested in participating. If they decline, no attempts will be made to convince them to participate.**

- g. What language will the prospective participant and the legally authorized representative understand? **English**

- h. What language will be used to obtain consent? **English**

- i. If any potential participants will be, or will have been, in a stressful, painful, or drugged condition before or during the consent process, describe the precautions proposed to overcome the effect of the condition on the consent process. If not, enter "None." **None**

- j. If any protocol-specific instruments will be used in the consenting process, such as supplemental handouts, videos, or websites, describe these here and provide a copy of each. If not, enter "None." **No supplemental handouts or instruments will be prepared by the research staff or provided to the patients by the research staff. Patients will be verbally instructed in the use of the products by research personnel. Additionally, patients may at their own discretion consult any instructional materials that are included inside or on the product packaging or made publically available by the manufacturers**

- k. How long will participants have between the time they are told about the protocol and the time they must decide whether to enroll? If not 24 hours or more, describe the proposed time interval and why the 24-hour minimum is neither feasible nor practical. **>24 hours**

22. Procedures to Protect Privacy

Describe how you will protect the privacy interest of the participants. Include how you will make sure others cannot overhear your conversation with potential participants and that individuals will not be publicly identified or embarrassed.

Individuals will not be publicly identified and all conversations pertaining to study participants will be held in private rooms.

23. Procedures to Maintain Confidentiality

- a. Describe how you will store research data to maintain confidentiality (both paper records and electronic data), including how access is limited. If data will be stored electronically anywhere other than a server maintained centrally by UAB, identify the department and all computer systems used to store protocol related data.

Data will be stored in the UAB hospital server. It will be accessed from hospital computers at Highlands. The file will only be accessible by directly involved investigators.

- b. Will any data from this protocol be given to any person, including the subject, or any group, including coordinating centers and sponsors? Yes No **If Yes, complete i-iii.**

i. Who will receive the data? **Data will be used for publication but it will be de-identified** ii. What data will be shared? **Study data**

iii. How will the data be identified, coded, etc.? **De-identified, coded with unique identifier**

number 24. Genomic Data Sharing (GDS)

FOR 200 Revised 4/23/2020 Page 15 of 16 07/29/19

Researchers who collect genomic data as part of a NIH grant funded after January 25, 2008 may be required to submit those data to a NIH database for broad scientific sharing. See [Genomic Data Sharing](#) in the IRB Guidebook for more information.

- a. Does this protocol involve the proposed submission of genetic data into genomic repositories created to share genetic information for research purposes? Yes No
- b. Will UAB be uploading the final genomic data to the central repository (e.g., dbGaP)? Yes No **If Yes to both a and b, submit a Detailed Data Sharing Plan to the IRB for review. This plan should include any known data use limitations and indicate whether aggregate-level data are appropriate for general research use. For guidance see the [NIH Genomic Data Sharing Policy](#).**
- c. Submit a copy of the NIH Institutional Certification Form.
To determine which certification form to include, answer i-ii.
- i. Was this protocol funded prior to January 25, 2015? Yes No • **If yes, and consent will be obtained, submit the [Extramural Institutional Certification - Before January 25 - With Consent](#).**
• **If yes, and consent will not be obtained, submit the [Extramural Institutional Certification - Before January 25 - Without Consent](#).**
- ii. Was this protocol funded after January 25, 2015? Yes No • **If yes, submit the [Extramural Institutional Certification - After January 25](#).**

25. Additional Information

In the space below, provide any additional information that you believe may help the IRB review the proposed research, or enter "None." **None**

Statistical Analysis Plan (SAP)

Preadmission Skin Wipe Use for Surgical Site Infection Prophylaxis in Adult Orthopaedic Surgery Patients

Last Update: 2/6/22

Principal Investigator

[name].
Associate Professor, Director of Clinical Research
Department of Orthopaedic Surgery
[name]
[name]

Protocol Identification Number

NCT03401749

Table of Contents:

1. Introduction.....	3
2. Study Design.....	3
3. Aims and objectives.....	3
4. Outcomes.....	3
4.1 Primary Outcomes.....	3
4.2 Secondary Outcomes.....	4
5. Populations to be Analyzed.....	4
6. Analyses.....	4

1. Introduction

The aim of this project was to assess in a single center randomized clinical trial (RCT) the use of the addition of 2 doses of 2% topical chlorhexidine gluconate wipes or topical Theraworx™ wipes to standard ChloroPrep skin preparation on patients undergoing orthopedic surgery procedures. Our objective is to test the hypothesis that administration of 2% topical chlorhexidine gluconate or topical Theraworx™ wipes (one dose the night before surgery and one on the day of surgery) will reduce the number of surgical site infections in patients undergoing orthopedic surgery procedures. Furthermore, we will explore whether the rate of surgical site infections from patients who utilized 2% topical chlorhexidine gluconate wipes significantly differs from those who utilized topical Theraworx™ wipes.

2. Study Design

This study is a randomized study that will include three groups: a control group, intervention group one that will be administered topical 2% chlorhexidine gluconate (CHG) wipes once the night before surgery and once on the day of surgery, and intervention group two that will be administered topical Theraworx™ wipes once the night before surgery and once on the day of surgery. After IRB is approved, 500 participants (160-180 per group) will be collected for the prospective study. Patients will be randomized into groups using a random number list generated in excel, which will be consulted by a research nurse or research fellow, who will instruct the patient in the use of the product related to their group assignment. [name] or [name] will perform orthopedic surgery on the participants without knowledge of their group assignment. Patients will be assessed for regimen compliance by survey. At clinic visits, patients will be assessed for the presence of surgical site infection, wound healing and scar formation, pain scores, and will be asked to complete a self-administered patient satisfaction questionnaire.

Patients will be assessed for signs and symptoms of infection at their two-week, six-week, and three-month clinical visits. We will continue follow up for one year postoperatively and compare the infection rate among the three groups.

3. Aims and Objectives

To study if 2% topical chlorhexidine gluconate or topical Theraworx™ wipes night before will reduce the number of surgical site infections in patients undergoing orthopedic surgery procedures.

4. Outcomes

This section will present the outcomes investigated to answer the study aims and objectives. The analyses are described in section 6 Analyses.

4.1 Primary Outcome

Infection rate between the three study cohorts. Signs and symptoms of infection will be measured at the 2-week, 6-week, and 3-month visits.

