- Include the [HIPAA Authorization](#) form, complete except for participant name and IRB protocol number, as the final page of the consent form

- PI requests waiver of authorization to use the information

- Attach [Waiver of Authorization and Informed Consent](#) form

NOTE: For BVAMC research, the BVAMC HIPAA authorization form or UAB HIPAA waiver form must be completed and submitted with the HSP.

PROPOSED RESEARCH

- The IRB will not accept grant applications and/or sponsor's protocols in lieu of the items as outlined below.
- Do not separate responses from items. Instead, insert your response to each item below the item, keeping the information in the order of this form.

14. Purpose - in nontechnical, lay language

a. Summarize the purpose and objectives of this protocol in one short paragraph.

The purpose of this protocol is to assess the effect of the addition of 2 doses of 2% topical chlorhexidine gluconate wipes or topical Theraworx™ wipes to standard ChloroPrep skin preparation on patients undergoing orthopedic surgery procedures. Our objective is to test the hypothesis that administration of 2% topical chlorhexidine gluconate or topical Theraworx™ wipes (one dose the night before surgery and one on the day of surgery) will reduce the number of surgical site infections in patients undergoing orthopedic surgery procedures. Furthermore, we will explore whether the rate of surgical site infections from patients who utilized 2% topical chlorhexidine gluconate wipes significantly differs from those who utilized topical Theraworx™ wipes. We hope to reduce the rate of surgical site infections with this intervention.

b. Describe how outcomes will be measured for this protocol.

Primary Outcome:

1. Clinical evaluation for presence of SSI (and standard of care culture etiology, if SSI is present) at all follow-up visits.

Secondary Outcomes:

- 1. Patient compliance survey: Patients will be assessed for compliance on the morning of surgery.**
- 2. Patient satisfaction: Patient satisfaction will be measured by asking each subject a single subjective question at baseline and each subsequent follow-up visit. Subjects will be asked “How satisfied are you with your orthopedic care?” Response options include: “Very Satisfied, Satisfied, Dissatisfied, and Very Dissatisfied”.**
- 3. Patient Pain scores: Patients will be asked to rate their pain on a 1-10 scale at each visit.**

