5.1 Populations

Control group: 160 patients who will receive only standard skin preparation prior to surgery.

Intervention group 1: 160 patients who will be administered 2% Chlorhexidine Gluconate wipes once on the night prior to surgery and once on the day of surgery in addition to standard skin preparation.

Intervention group 2: 180 patents who will be administered Theraworx™ wipes once on the night prior to surgery and once on the day of surgery in addition to standard skin preparation.

Intention-to-Treat

All randomized study subjects. This will be the primary population for analysis.

Per Protocol

All randomized study subjects completing the whole study period (complete cases). For a specific analysis, study subjects with missing data on any of the variables in the model will be excluded from the analysis.

6. Analyses

The primary analysis will compare intervention groups and their respected rate of infection between baseline, 2-weeks, 6-weeks, and 3 months using a linear mixed model. Difference in infection rate from baseline to time points where it is measured during the study will be the dependent variable. Study subjects will be considered as random effects, treatment group and visit number as fixed effects.

Patient compliance was monitored via patient questionnaires on the date of surgery. If compliance rate differed significantly, it would be labeled as a confounding factor.

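### No rule captures or carries forward a surgical site infection that is diagnosed and resolved between visits, so the visit-based primary outcome may undercount the events the trial aims to reduce

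*SAP*

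**What the plan says.** The hypothesis in Protocol 14.a and SAP section 1 concerns how many SSIs occur, so each patient either has one or does not.

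The measurement text is organised by visit:

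- SAP 4.1, after naming the infection rate as the primary outcome: "Signs and symptoms of infection will be measured at the 2-week, 6-week, and 3-month visits".
- SAP section 2: "Patients will be assessed for signs and symptoms of infection at their two-week, six-week, and three-month clinical visits". The same section sets the place of assessment: "At clinic visits, patients will be assessed for the presence of surgical site infection, wound healing and scar formation, pain scores".
- Protocol 14.b: "Clinical evaluation for presence of SSI (and standard of care culture etiology, if SSI is present) at all follow-up visits". It does not number or date those visits.

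The analysis is also organised by visit. SAP section 6 compares the "rate of infection between baseline, 2-weeks, 6-weeks, and 3 months using a linear mixed model", with visit number as a fixed effect, and adds: "Difference in infection rate from baseline to time points where it is measured during the study will be the dependent variable".

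One sentence in SAP section 2 reaches further: "We will continue follow up for one year postoperatively and compare the infection rate among the three groups". It gives no visit times and no method of finding infections after 3 months.

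Neither document defines a variable for any SSI since surgery, a question about the time since the last visit, a chart check, or the handling of SSIs found at unscheduled visits, readmissions, reoperations or outside providers. By contrast, SAP 4.2 says explicitly that patients will be asked about side effects.

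**The concern.** Status at a visit and occurrence since surgery are different quantities. An SSI can start after one visit, bring the patient in for care, and clear before the next. It belongs in a count of SSIs, yet an assessor who records only what is present at the scheduled visit has nothing to enter.

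The protocol's Benefits section (item 18) says SSIs often lead to longer stays, more antibiotics and even revision surgery. Such care need not fall on a scheduled visit. The spaces between the three visits are about 28 and 49 days.

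Two things are at stake. Assessors may apply different rules, one asking what has happened since the last visit and another scoring the wound in front of them. And with very few events expected, each one lost matters to the precision of the comparison.

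**Working it through.** The plan states no figure on this point that could be reproduced: it has no capture rate, power calculation or target effect. The check asks what the stated rule records, then how much it could lose.

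**Step 1: what the model receives.** Eligibility (Protocol 16.d) requires no clinical signs of skin infection and excludes other infections, so infection status at baseline should be 0. The difference from baseline at a visit is then simply the status at that visit. Take an SSI that starts on day 20 and shows signs for an assumed 14 days, so that it clears on day 34. With visits on days 14, 42 and 91, status at the visits is 0, 0, 0. A patient who was never infected has the same record. Nothing in SAP section 6 carries an intervening event forward.

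**Step 2: share captured by visits alone.** Assume visits on days 14, 42 and 91 and signs lasting D days. Onset at day o is captured if o ≤ t ≤ o + D for some visit t. Onset days captured:

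- D = 10: days 4–14, 32–42, 81–91
- D = 14: days 0–14, 28–42, 77–91
- D = 21: days 0–14, 21–42, 70–91
- D = 28: days 0–42, 63–91

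| D (days) | Onset uniform over days 0–30 | Onset uniform over days 0–91 |
|---|---|---|
| 10 | 10/30 = 33% | 30/91 = 33% |
| 14 | (14 + 2)/30 = 53% | 42/91 = 46% |
| 21 | (14 + 9)/30 = 77% | 56/91 = 62% |
| 28 | 30/30 = 100% | 70/91 = 77% |

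As a sensitivity check, put 50%, 35% and 15% of onsets in the three gaps of L = 14, 28 and 49 days. The missed share is the weighted sum of max(0, 1 − D/L). For D = 14 it is 0.50 × 0 + 0.35 × 0.50 + 0.15 × 0.714 = 28%. For D = 28 it is 0.15 × 0.429 = 6%.

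D and the onset pattern are assumptions; the documents supply neither.

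**Step 3: expected events.** Protocol item 18 says "surgical site infections occur in about 2% of all patients undergoing orthopedic procedures". Applied to the planned arms (Protocol 16.e, SAP 5.1):

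- control: 160 × 0.02 = 3.2
- chlorhexidine: 160 × 0.02 = 3.2
- Theraworx: 180 × 0.02 = 3.6
- total: 500 × 0.02 = 10

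**Step 4: cost in precision.** Assume a halving from 2% to 1%, 160 per arm and two-sided alpha 0.05; none of these test settings is in the documents. With the normal approximation for two proportions, power = Φ[(Δ − 1.96 × SE₀)/SE₁], where SE₀ uses the pooled rate and SE₁ the separate rates. Full capture: Δ = 0.010, SE₀ = SE₁ = 0.0136, power about 11%. Missing 25% of events equally in both arms (1.5% vs 0.75%) gives about 9%. Missing 50% (1% vs 0.5%) gives about 7.5%.

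**The case against.** The strongest reply is that the documents are silent rather than wrong. A reader might infer that an SSI resolved between visits is scored as no infection. No sentence says so. SAP 4.1 measures symptoms as well as signs, and symptoms come from talking to the patient. Protocol 14.b covers all follow-up visits, which on plain wording could include an unscheduled return to the clinic. Participants are the surgeons' own patients, followed in the Highlands clinics, so those clinics may well know of an infection they treated. Staff follow-up instructions (Protocol 3.g) and any questionnaires (17.f) are not in the file, and the ticked data sources in 13.d cannot be read, so use of hospital records can be neither confirmed nor excluded.

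A reader might also conclude that about half the events would be lost, or that the comparison would be biased. The first depends on choosing D near 14 days; by the same formula, 28 days gives 77% to 100% capture. The second needs loss that differs by arm, and the documents show no mechanism for it. Equal proportional loss leaves the risk ratio unchanged. Power is also very low with full capture, so sample size dominates.

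Most of this stands. It makes the Step 2 losses upper bounds for the assumed D and onset, and it limits the point to undercounting and lost precision. It does not remove the gap. The rule for counting a primary event belongs in the outcome definition, not in clinic custom. An unscheduled visit that fits Protocol 14.b still has no time point in the SAP section 6 model. The one-year sentence has no method of capture, and the primary model ends at 3 months.

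**Conclusion.** The concern holds in a limited form, as a should-fix. The objective counts SSIs, while the stated outcome and model use infection status at visits, and no rule captures or carries forward an SSI that is diagnosed and resolved in between. Read literally, such an event may be missed from the primary analysis.

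The size of the loss cannot be derived from the documents. For assumed durations of 10 to 28 days, visit-only capture runs from about 33% to 77% or from 33% to 100%, depending on the assumed onset period, and the actual loss is smaller if visits take a history or charts are reviewed. With about 10 SSIs expected in total, any loss costs precision. The documents do not support saying that these SSIs are definitely coded as absent, that a particular number will be lost, or that one arm will be favoured.

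**What to change.** 1. In SAP 4.1 and Protocol 14.b, define the primary outcome as a per-patient yes/no indicator of any SSI diagnosed from surgery to a stated time point, at any scheduled or unscheduled contact, with its date.
2. In SAP section 6, make that indicator the dependent variable in place of the per-visit difference from baseline.
3. Reconcile the 3-month window of SAP 4.1 and section 6 with the one-year comparison in SAP section 2: say which is primary and how infections are found over that period.
4. At each existing visit, ask every patient in all arms the same question about the interval since last seen: wound infection diagnosed, antibiotics for the wound, emergency visit, readmission or return to theatre. Check the hospital record for the same interval.
5. SAP section 6 describes compliance monitoring in the past tense, so visits may already be complete. If so, do the record check retrospectively, identically in all arms and without knowledge of assignment.

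The cost is a wording change in both documents, one visit question and a chart check, with no new visits. The small downside is that events treated by outside providers rest on patient report and may need confirmation from records; a retrospective check of the hospital record alone would not find them.
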